9.4 CRI Reporting Requirements

Adverse events can be spontaneously reported or elicited during open-ended questioning, examination, or evaluation of a subject. To prevent reporting bias, subjects should not be questioned regarding the specific occurrence of one or more adverse events.

If known, the diagnosis of the underlying illness or disorder should be recorded, rather than its individual symptoms. The following information should be captured for all AEs: onset, duration, intensity, seriousness, relationship to study drug, action taken, and treatment required. If treatment for the event was administered, it should be recorded in the medical record. The Sponsor-Investigator must retain and notify the IRB with any additional information requested, notably for reported deaths of subjects.

In accordance with relevant local legislation or regulations, including the applicable US FDA Code of Federal Regulations, the Sponsor-Investigator will report all serious adverse events, including reports of pregnancies, overdose and cancer that may or may not be associated with an adverse event to the FDA via filing of a FDA MedWatch 3500A form.

Assessment of expectedness for SAEs will be determined using reference safety information specified in the Investigator's Brochure.

Gilead Sciences, Inc. will provide timeline notification of relevant SUSAR reports. The Sponsor-Investigator must ensure notification of all study staff of the contents of the SUSAR reports, and will notify the IRB/IEC of SUSAR reports in accordance with the IRB/IEC policy.

9.5 Clinical Laboratory Abnormalities and Other Abnormal Assessments as Adverse Events or Serious Adverse Events

Laboratory abnormalities are usually not recorded as AEs or SAEs. However, laboratory abnormalities (e.g. clinical chemistry, hematology, and urinalysis) independent of the underlying medical condition that require medical or surgical intervention or lead to investigational medicinal product interruption or discontinuation must be recorded as an AE, as well as an SAE, if applicable. In addition, laboratory or other abnormal assessments (e.g., electrocardiogram, X-rays, vital signs) that are associated with signs and/or symptoms must be recorded as an AE or SAE if they meet the definition of an AE (or SAE) as described in Sections 9.1.1 and 9.1.2. If the laboratory abnormality is part of a syndrome, record the syndrome or diagnosis (i.e., anemia) not the laboratory result (i.e., decreased hemoglobin).

Severity should be recorded and graded according to the GSI Grading Scale for Severity of AEs and Laboratory Abnormalities (Appendix 4). For AEs associated with laboratory abnormalities, the event should be graded on the basis of the clinical severity in the context of the underlying conditions; this may or may not be in agreement with the grading of the laboratory abnormality.

9.6 Subject Stopping Rules

The Medical Monitor should be consulted prior to dose discontinuation of Epclusa unless the Investigator believes that immediate action is warranted to ensure the continued safety of the subject.

Due to a clinical or laboratory event, administration of all study drug(s) may be discontinued. There is no option for Epclusa dose reduction. If Epclusa is stopped for toxicity, it must not be restarted Post-Treatment Weeks 4 and 12 Visits must also be scheduled.

Subjects who meet any of the following laboratory criteria must stop all study drug(s):

- Elevation of ALT and/or AST >5x Baseline/Day 1 or nadir, confirmed by immediate repeat testing

- Abnormal elevation of ALT >3x Baseline/Day 1 and total bilirubin >2 x ULN, confirmed by immediate repeat testing
- Elevation of ALT >15 x ULN, confirmed by immediate repeat testing
- Any Grade 3 or greater rash associated with constitutional symptoms
- Any Grade 4 adverse event or laboratory abnormality assessed as related to Epclusa

9.7 Special Situations Reports

9.7.1 Definitions of Special Situations

Special situation reports include all reports of medication error, abuse, misuse, overdose reports and pregnancy reports regardless of an associated AE. These also include reports of adverse reactions in infants following exposure from breastfeeding, and reports of adverse reactions associated with product complaints and reports arising from occupational exposure.

- A pregnancy report is used to report any pregnancy following maternal or paternal exposure to the medicinal product.
- Medication error is any unintentional error in the prescribing, dispensing, or administration of a medicinal product while in the control of the health care provider, subject, or consumer.
- Abuse is defined as persistent or sporadic intentional excessive use of a medicinal product by a subject.
- Misuse is defined as any intentional and inappropriate use of a medicinal product that is not in accordance with the protocol instructions or the local prescribing information.
- An overdose is defined as an accidental or intentional administration of a quantity of a medicinal product given per administration or cumulatively which is above the maximum recommended dose as per protocol or in the product labeling (as it applies to the daily dose of the subject in question). In cases of a discrepancy in drug accountability, overdose will be established only when it is clear that the subject has taken the excess dose(s). Overdose cannot be established when the subject cannot account for the discrepancy except in cases in which the Investigator has reason to suspect that the subject has taken the additional dose(s).
- Product complaint is defined as complaints arising from potential deviations in the manufacture, packaging, or distribution of the medicinal product.

9.8 Reporting Special Situations

9.8.1 Instructions for Reporting Pregnancies

Any pregnancy of a woman participant or female partner of a male study participant should be immediately reported to the Medical Monitor and Sponsor-Investigator. All pregnancies will be reported to the IRB/IEC within 24 hours of notification, and followed-up through the end of the pregnancy. Pregnancy outcomes will be recorded and reported to the IRB/IEC.

The Sponsor-Investigator will collect information on all pregnancies that are identified after the subject first consents to participate in the study (i.e., signs the informed consent) and throughout the study, including the post study drug follow-up period.

The pregnancy itself is not considered an AE nor is an induced elective abortion to terminate a pregnancy without medical reasons.

Any premature termination of pregnancy (e.g., a spontaneous abortion, an induced therapeutic abortion due to complications or other medical reasons) will be reported by the Sponsor-Investigator within 24

hours as an SAE to the IRB/IEC. The underlying medical reason for this procedure should be recorded as the AE term.

A spontaneous abortion is always considered to be an SAE and will be reported as an SAE to the IRB/IEC.

Furthermore, any SAE occurring as an adverse pregnancy outcome post study will be reported to the IRB/IEC.

The subject should receive appropriate monitoring and care until the conclusion of the pregnancy. The outcome of the pregnancy, whether the end of the pregnancy occurs after the study has been completed or during study participation, will be recorded. Outcomes that meet the definition of reportable to the IRB/IEC and FDA will be reported by CRI.

Pregnancies of female partners of male study subjects exposed to the study drug will also be followed closely and relevant information will be collected. Monitoring of the partner will continue until the conclusion of the pregnancy. The outcome will be collected and may be reported to the IRB/IEC and FDA.

Refer to the study operations manual for pregnancy information collection and reporting instructions.

AEs and SAEs related to the pregnancy that affect the mother and/or the fetus will be reported via FDA MedWatch Form 3500a when the Sponsor-Investigator assesses the adverse even to be possibly associated with the study product used during pregnancy. Instances of reportable pregnancy related SAE/AEs include but are not limited to: fetal death, miscarriage, spontaneous abortion, fetal adverse reaction, congenital anomaly and defect.

Additional reporting of pregnancy and outcomes to the study drug manufacturer may also occur.

9.8.2 Reporting Other Special Situations

All other special situation reports must be reported on the special situations report form and forwarded to the CRI Medical Monitor within 24 hours of becoming aware of the situation. These reports must consist of situations that involve study drug, but do not apply to concomitant medications. Except for situations that result in AEs, special situations involving concomitant medications will not be reported. Any inappropriate use of medications prohibited by this protocol should not be reported as "misuse," but may be more appropriately documented as a protocol deviation.

Refer to the study operational manual for full instructions on the mechanism of special situation capture and collection.

Note: All clinical sequelae in relation to these special situation reports will be reported as AEs or SAEs at the same time using the AE eCRF and/or the SAE report form. Details of the symptoms and signs, clinical management, and outcome will be reported, when available.

In addition to reporting SAEs and special situations to the IRB/IEC and regulatory authorities per the applicable recommendations and regulations, the Sponsor-Investigator will notify Gilead Sciences, Inc. of all safety information, including SAEs and special situation reports within 15 days of awareness of the safety information and in accordance with applicable laws and regulations. All reports will be addressed to Gilead at the attention of:

Gilead Sciences, Inc.
Drug Safety & Public Health
[name]
[name]
[contact]

10 STATISTICAL CONSIDERATIONS

10.1 Analysis Objectives and Endpoints

10.1.1 Analysis Objectives

Primary Objective:

- To assess the effectiveness, as measured by SVR12, of HCV treatment with Epclusa administered by an internal medicine physician/licensed buprenorphine/naloxone provider during regularly scheduled office visits for buprenorphine/naloxone maintenance therapy.

Secondary Objectives:

- To assess the impact of HCV treatment on health-related quality of life among subjects on buprenorphine/naloxone therapy.
- To assess adherence to Epclusa Therapy in subjects administered treatment in the context of visits to a buprenorphine/naloxone clinic.

Exploratory Objective:

- To design and assess a curriculum and mentorship program to support internal medicine providers with managing HCV infection. The curriculum for the purpose of this study will be tailored to the management of HCV genotype 1 and treatment with Epclusa.

10.1.2 Primary Endpoint

The primary efficacy endpoint is rate of SVR-12 (HCV RNA <LLOQ 12 weeks after discontinuation of study treatment).

10.1.3 Secondary Endpoints

Secondary efficacy endpoints include the following:

- Adherence to Epclusa expressed as percentage of patients who miss 1-4% of doses, 5-9% of doses, 10-20% of doses and > 20% of doses
- Overall ratio of doses taken/doses prescribed in the study population
- Change in scores of QOL questionnaires

10.1.4 Safety Endpoints

The primary safety endpoint is any AE leading to permanent discontinuation of study drug(s).

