3.2 Epclusa

Epclusa is a two-drug fixed-dose combination product that contains 100 mg of velpatasvir and 400 mg of sofosbuvir in a single tablet. The recommended dosage of Epclusa is one tablet taken orally once daily with or without food for 12 weeks. Velpatasvir is a pangenotypic HCV NS5A inhibitor and sofosbuvir is a pangenotypic nucleotide inhibitor of HCV NS5B RNA-dependent RNA polymerase.

Epclusa was approved by the FDA in 2016 for the treatment of adult patients with chronic hepatitis C infection genotypes 1, 2, 3, 4, 5, and 6. It is recommended as first line therapy for treatment naïve and pegylated-ribavirin-experienced adults with chronic hepatitis C infection genotypes 1-6 (AASLD and IDSA HCV Guidelines, October, 2016). Safety and tolerability data for Epclusa is based on data from three Phase 3 clinical trials (ASTRAL-1, ASTRAL-2, and ASTRAL-3) which enrolled a total of 1035 subjects who either did not have cirrhosis or who had compensated cirrhosis (Epclusa Package Insert).

Overall, 0.2% of subjects in the three studies discontinued Epclusa due to adverse events.

The most common adverse reactions ($\geq 10\%$) during 12 weeks of treatment with Epclusa were headache and fatigue.

ASTRAL-1 was a randomized placebo-controlled trial which enrolled 740 subjects with genotypes 1, 2, 4, 5, and 6 chronic HCV. Nineteen percent of these subjects had compensated cirrhosis and 32% were treatment experienced. The table below lists adverse reactions (adverse events assessed as causally related by the Investigator, all grades) observed in $\geq 5\%$ of subjects in ASTRAL-1. The majority of adverse reactions were of severity grade 1. Importantly, each of these reactions occurred at a similar frequency or more frequently in the control arm, with the exception of asthenia which occurred in 5% subjects on Epclusa and 3% of subjects on placebo.

Reaction	Frequency in ASTRAL-1
Headache	22%
Fatigue	15%
Nausea	9%
Asthenia	5%
Insomnia	5%

Co-administration of amiodarone with Epclusa is not recommended because post-marketing cases of symptomatic bradycardia, as well as fatal cardiac arrest and cases requiring pacemaker intervention, have been reported when amiodarone is co-administered with sofosbuvir.

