5.5 Treatment Discontinuation Criteria

The Medical Monitor should be consulted prior to subject discontinuation when medically feasible. Study drug must be discontinued in the following instances:

- Unacceptable toxicity, as defined in Section 9 of the protocol, or toxicity that, in the judgment of the Sponsor-Investigator or Sub-Investigator(s), compromises the ability to continue study-specific procedures or is considered to not be in the subject's best interest
- Pregnancy of female subject
- HCV efficacy failure as defined in Section 5.3
- Significant protocol violation
- Subject request to discontinue for any reason; it is important to determine and document whether the withdrawal of consent is primarily due to an adverse event (AE), lack of efficacy, or other reason
- Discontinuation of the study at the request of CRI, regulatory agency, or an Institutional Review Board (IRB)/Independent Ethics Committee (IEC)

If a subject meets discontinuation criteria during treatment, an Early Termination Visit will be required (Section 8.2.4). Early Termination Visits should be scheduled as soon as possible following discontinuation of treatment. Subjects that discontinue treatment early are still required to complete Post-Treatment Weeks 4, and 12 Visits.

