8.6 Assessments for Premature Discontinuation from Study Dosing

If a subject discontinues study drug dosing (for example, as a result of an AE), every attempt should be made to keep the subject in the study and continue to perform the required study-related follow-up and procedures. If this is not possible or acceptable to the subject or Sponsor-Investigator, the subject may be withdrawn from the study.

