10.6 Secondary Analysis

Adherence:

- Percentage of patients who miss 1-4% of doses, 5-9% of doses, and 10-20% of doses and > 20% of doses and the 95% confidence interval will be reported. The percentage of doses taken out of total doses prescribed will be reported with its 95% confidence interval.

Quality of Life:

- Mean in QOL scores from baseline to EOT will be reported with its 95% confidence interval.

Safety Analysis

- All safety data collected on or after the first dose of study drug administration up to 30 days after the last dose of study drug will be summarized. **All AE's of each level severity will be reported with the number and percent who experienced them. The number and percent of patients who stopped the study because of SAE's will be reported, with the 95% confidence interval.**

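### The primary safety endpoint (any AE leading to permanent drug discontinuation) has no estimate of its own; the one discontinuation estimate planned counts a different event, stopping the study because of an SAE

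*Combined protocol and SAP*

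**What the plan says.** Section 10.1.4 names a single primary safety endpoint: "The primary safety endpoint is any AE leading to permanent discontinuation of study drug(s". The definition covers serious and non-serious events alike, and the action it refers to is stopping the drug.

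The safety part of section 10.6 plans three outputs:

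- a general summary of safety data from first dose, "up to 30 days after the last dose of study drug will be summarized";
- the number and percent of subjects with AEs at each severity level;
- one discontinuation estimate: "The number and percent of patients who stopped the study because of SAE's will be reported", with a 95% confidence interval.

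Section 10.2.1.2 supplies the denominator (subjects with at least one dose). On data capture, section 9.4 states: "The following information should be captured for all AEs: onset, duration, intensity, seriousness, relationship to study drug, action taken, and treatment required".

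**The concern.** Every other named endpoint has a matching output: SVR12 in 10.5, adherence and quality of life in 10.6, provider comfort in 10.7. The primary safety endpoint does not. The severity table does not sort AEs by whether drug was stopped, and the line that carries an interval describes another event.

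The two counts can disagree. A subject who stops Epclusa for a non-serious AE and completes follow-up is an event under 10.1.4 and not under 10.6. In the other direction, a subject who finishes 12 weeks of drug and then leaves follow-up because of an SAE is an event under 10.6 and not under 10.1.4. A reader of the report could take the 10.6 figure for the primary safety result when it is not. The SVR12 analysis, the stopping rules and SAE reporting are unaffected.

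**Working it through.** The plan gives no figure to reproduce: about 20 subjects are planned, with no power, precision or safety threshold stated. The check is therefore a comparison of texts, followed by an illustration of size.

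**Comparison of the two definitions**

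| | 10.1.4 (endpoint) | 10.6 (estimate with interval) |
|---|---|---|
| Event | any AE | SAE only |
| Action | permanent stop of study drug | stop of the study |
| Statistic | none stated | number, percent, 95% interval |

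**Does the protocol treat these as different things?**

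1. *Drug and study.* Section 5.5 says: "Subjects that discontinue treatment early are still required to complete Post-Treatment Weeks 4, and 12 Visits". Section 8.6 says that after a drug stop "every attempt should be made to keep the subject in the study", and treats withdrawal from the study as a separate step. Section 9.6 also calls for the Week 4 and Week 12 post-treatment visits. A subject who stops drug and follows the protocol has not stopped the study.
2. *AE and SAE.* The mandatory drug-stopping list in 9.6 includes "Any Grade 3 or greater rash associated with constitutional symptoms" and a confirmed ALT or AST rise above 5 times baseline. Neither has to meet the definition of serious in 9.1.2. Sections 9.1.3 and 9.5 say that a laboratory abnormality leading to drug discontinuation is recorded as an AE, and as an SAE only where that applies. The protocol therefore allows for non-serious events that stop drug.

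**Size**

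Inputs: n = 20 (sections 5.1 and 6.1 say approximately 20; exactly 20 dosed is an assumption), and p = 0.002 from section 3.2: "Overall, 0.2% of subjects in the three studies discontinued Epclusa due to adverse events".

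Exact (Clopper-Pearson) 95% intervals, n = 20:

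- 0/20: lower limit 0; upper limit 1 − 0.025^(1/20) = 16.8%.
- 1/20 = 5%: lower limit 1 − 0.975^(1/20) = 0.1%; upper limit, the 0.975 quantile of Beta(2, 19), = 24.9%.

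So one non-serious drug-stopper who completes follow-up gives 1/20 (0.1% to 24.9%) for the endpoint and 0/20 (0% to 16.8%) in the 10.6 line. The reverse case swaps the two.

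Chance of at least one endpoint event, 1 − (1 − p)^20:

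| p | Source | Chance of at least 1 in 20 |
|---|---|---|
| 0.2% | section 3.2 | 1 − 0.998^20 = 3.9% |
| 1% | assumption | 1 − 0.99^20 = 18.2% |
| 2% | assumption | 1 − 0.98^20 = 33.2% |

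At p = 0.002 the chance of two or more is 1 − 0.998^20 − 20 × 0.002 × 0.998^19 = 0.03925 − 0.03851 = 0.07%. The 3.9% is an upper limit on the chance that the 10.6 line misses an endpoint event at that rate, because some events would be SAEs that also end study participation.

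**The case against.** The strongest reply is that the endpoint is well provided for apart from one line. It has a definition, a denominator and the data items to derive it, and the general sentence in 10.6 would let a competent analyst tabulate it. In a single-arm pilot of about 20 with no hypothesis or decision tied to safety, any AE-related drug stop would be visible case by case, and at the cited rate there would most likely be none. This stands as an argument about weight. It does not close the gap, because the general sentence names neither the endpoint nor a statistic, while a different event gets both.

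A second reply is that stopping the study may be loose wording for stopping drug. That is possible, but non-serious AEs would still be left out.

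Three qualifications are fair:

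- Section 8.6 permits withdrawal from the study where staying is not possible or acceptable, so follow-up after a drug stop is intended but not guaranteed.
- The 9.6 examples could be judged medically important, and so serious, in a given case. They need not be.
- The reverse case is the weaker one. If the SAE line shares the 30-day limit of the general summary, an exit later in follow-up would not count in 10.6 either. The concern rests mainly on the non-serious drug stop.

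**Conclusion.** The concern holds. The plan names a primary safety endpoint, states no estimate for it, and gives its only discontinuation interval to an event that differs in both seriousness and action. The AE-against-SAE difference remains under any reading of the 10.6 wording.

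The size is modest: one subject classified differently moves the result between 0% and 5%, and the upper 95% limit between 16.8% and 24.9%. These figures assume 20 dosed subjects and exact intervals, since the plan names no interval method. The 3.9% chance of any event assumes that the 0.2% trial rate carries over to this clinic population. The 1% and 2% rates are illustrations only. The mismatch should be corrected even if no event is expected, because with zero events the reported interval would still describe something other than the stated endpoint.

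**What to change.** Add to the safety analysis in 10.6: *the number and percent of subjects who received at least one dose and permanently discontinued Epclusa because of any AE, serious or non-serious, with a 95% confidence interval*. Keep withdrawal from the study because of SAEs as a separate, labelled line, and state the time window it covers. Name the interval method; an exact interval suits about 20 subjects, though the repair does not depend on that choice.

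The cost is one more line of analysis. Seriousness and action taken are already to be recorded for each AE, and the denominator is already defined. No visit, assessment or clinical rule changes. The reported figure may be slightly less favourable than the 10.6 line alone would show.

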10.1.5 Other Endpoints of Interest

The Internal Medicine Physician's change in comfort level with providing HCV care over course of study.

